5.4 Secondary outcomes10)
5.5 Process measures)
5.6 Safety outcome measures10)
5.7 Graphs and other data summaries1	1
5.8 Plan in case of non-convergence of analysis models12	2
5.9 Plan in case of over-stratification12	2
5.10 Subgroup analyses13	3
5.11 Per-protocol analysis	3
6. Sensitivity Analysis	1
References	õ
Appendix 1: Deriving outcomes and variables1	7
Appendix 2: Dummy tables	L

1. Administrative information

Trial registration number: ISRCTN registry – ISRCTN56012545

This SAP is based on protocol version 1.6 (date: 10/04/2017)

Changes from previous version of SAP

- The previous version of the SAP inadvertently omitted the category 'resection of oesophagus (non-obesity surgery)' as one of the categories of the minimisation variable surgical procedure category. This has been corrected in the randomisation and analysis sections.
- The previous SAP included the outcome 'Mechanical ventilation (invasive or non-invasive) within 30 days of randomisation' this has been changed to 'Postoperative mechanical ventilation (invasive or non-invasive) within 30 days of randomisation', to clarify that this outcome refers to mechanical ventilation during the postoperative period
- Section 5.1 was updated to clarify that patients who were enrolled in PRISM for a repeat surgery despite previous enrolment would be included in the analysis
- In section 5.2.5 we have separated the category 'Administration of CPAP for less than 4 hours or with significant interruption for a patient in the treatment group (continuous interruption of more than 15 minutes would usually be considered prolonged).' into two separate categories: (i) Administration of CPAP for less than 4 hours duration in the treatment group; and (ii) Administration of CPAP with significant interruption for a patient in the treatment group (continuous interruption of more than 15 minutes would usually be considered prolonged).
- We updated section 5.3 (describing the analysis of the primary outcome) to state that any categories with fewer than 15 patients for the variable *planned surgical procedure* will be combined with the category 'other intra-peritoneal surgery' for analysis
- We updated section 5.3 (describing the analysis of the primary outcome) to state that missing baseline covariates will be handled using mean imputation or the missing indicator approach for analysis
- We added a per-protocol analysis using inverse-probability weighting for the primary outcome and following secondary outcomes: (a) pneumonia within 30 days of randomisation; (b) endotracheal re-intubation within 30 days of randomisation; (c) all-cause mortality within 30 days of randomisation. Full information is given in section 5.11.
- We added a new appendix (appendix 1) which details how at least 'one' comorbid disease, primary and secondary outcomes will be derived.
- We added a section on summarising CPAP information for the CPAP group (section 5.2.4)
- We added a plan in case of over-stratification when adjusting for covariates in the primary and secondary analysis models (section 5.9)

2. Introduction

2.1 Background

Prevention of Respiratory Insufficiency after Surgical Management (PRISM) is an international, multicentre, parallel group, randomised controlled trial which aims to evaluate the clinical effectiveness of early post-operative continuous positive airway pressure (CPAP) administered as routine care compared to usual care in patients undergoing major abdominal surgery. The planned sample size is 4800 patients.

2.2 Purpose of statistical analysis plan

This document outlines the statistical analysis planned for the trial. It is important to set these out and to agree them in advance of inspecting the outcome data for the trial, so that data-derived decisions in the analysis are avoided. Any exploratory, post hoc or unplanned analysis will be clearly identified as such in the respective study analysis report. This SAP does not cover the cost and cost-effectiveness analysis, or the quality adjusted life years (QALY) at one-year after randomisation; these analyses will be planned in separate documents.

2.3 Inclusion/Exclusion criteria

Inclusion Criteria

Patients aged 50 years or over undergoing elective major intra-peritoneal surgery using an open surgical technique.

Exclusion Criteria

- Inability or refusal to provide informed consent
- Anticipated requirement for invasive or non-invasive mechanical ventilation for at least four hours after surgery as part of routine care
- Pregnancy or obstetric surgery
- Previous enrollment in PRISM trial
- Participation in a clinical trial of a treatment with a similar biological mechanism or related primary outcome measure

3. Outcome Measures

3.1 Primary outcome

• Composite endpoint of pneumonia, endotracheal re-intubation or death within 30 days of randomisation.

3.2 Secondary outcome

- Pneumonia within 30 days of randomisation
- Endotracheal re-intubation within 30 days of randomisation
- All-cause mortality within 30 days of randomisation
- Postoperative infection within 30 days of randomisation
- Postoperative mechanical ventilation (invasive or non-invasive) within 30 days of randomisation
- All-cause mortality within one year of randomisation

3.3 Process measures

In addition, we will use the following process measures (i.e. non-patient centred outcome measures), to facilitate comparison with other research:

- Re-admission to hospital within 30 days of randomisation
- Days in critical care (defined as either level 2 or level 3 critical care)
- Duration of hospital stay (days)

3.4 Safety outcome measures

Safety outcomes will quantify harm associated with CPAP (appendix). Presence or absence of the following pre-defined adverse events will be measured within 24 hours of the end of surgery in patients in the treatment group only:

- Interface intolerance due to excessive air leaks
- Pain
- Cutaneous pressure sore or pressure area
- Claustrophobia
- Oro-nasal dryness
- Hypercapnia
- Haemodynamic instability
- Vomiting
- Aspiration of gastric contents
- Other harm assessed as probably or definitely related to CPAP

4. Study Methods

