5.6 Safety outcome measures

Each safety outcome measured will be summarised for patients in the CPAP group by the number (%). All patients with a recorded outcome will be included in the summary. In addition to this, 'other'

adverse events will be reported separately if prevalence is more than 1% across all participants in the trial.

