5.7 Graphs and other data summaries

- The flow of study participants will be displayed in Consolidated Standards of Reporting Trials (CONSORT) diagram.
- 30-day and one-year survival of patients will be presented for both groups using Kaplan-Meier survival curves.
- Investigator self-assessment of blinding by treatment allocation will be presented as number (%).
- Duration of level 2 and 3 critical care stay within 30 days of randomisation for patients admitted to a critical care unit will be presented as mean (SD) and median (IQR).
- Data describing a predefined list of the most common post-operative complications occurring within 30 days of randomisation will be collected for all patients.

The number and percentage of patients experiencing each of the following complications will be presented by (a) treatment allocation; (b) treatment allocation and Clavien-Dindo (CD) grade (I-II vs III-V); and (c) treatment allocation and CPAP delivery method for those in the CPAP group only. These summaries will not be subjected to any statistical testing. These complications are:

Respiratory complications:

- o Pneumonia
- o Pleural effusion
- o Pneumothorax
- o Bronchospasm
- Aspiration pneumonitis
- Acute Respiratory Distress Syndrome (ARDS)

Infective complications:

- Surgical site infection (superficial)
- Surgical site infection (deep)
- Surgical site infection (organ space)
- Urinary tract infection
- Infection, source uncertain
- Laboratory confirmed blood stream infection

Cardiac complications:

- Myocardial infraction
- o Arrhythmia
- Cardiogenic pulmonary oedema
- o Cardiac arrest with successful resuscitation

Other complications:

- Acute kidney injury
- Pulmonary embolism
- o Stroke
- Acute psychosis or delirium
- o Bowel infarction
- o Anastomotic leak
- Perforation of viscus (e.g. bowel, gall bladder etc.)
- Postoperative haemorrhage
- Other postoperative haemorrhage
- Any other complication

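### For the non-specific safety items, recording in the CPAP arm alone gives an incidence and not the harm associated with CPAP; the two-arm complications that could show excess harm have no between-arm estimate

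*SAP*

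**What the plan says.** Section 3.4 gives the aim: "Safety outcomes will quantify harm associated with CPAP". It then restricts collection: presence or absence of the listed events "will be measured within 24 hours of the end of surgery in patients in the treatment group only". Nine events are named. The tenth item is "Other harm assessed as probably or definitely related to CPAP", and it is the only one for which the SAP asks for a judgement of relatedness. Section 3.4 also points to an appendix. The SAP's own two appendices contain outcome derivations and dummy tables, with no definitions of the safety events.

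Section 5.6 plans the analysis: "Each safety outcome measured will be summarised for patients in the CPAP group by the number" and percentage. Dummy Tables 12 to 14 have CPAP columns only.

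Section 5.7 covers a different set of events, for which "complications occurring within 30 days of randomisation will be collected for all patients". Tables 6 and 8 show them by allocated arm, and Table 8 also splits them by Clavien-Dindo grade. On these, "These summaries will not be subjected to any statistical testing". Neither table has a column for a difference or an interval. Section 5.1 promises effect estimates with 95% CIs for primary and secondary outcomes only.

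**The concern.** Harm associated with a treatment is a contrast: the risk with it minus the risk without it. Some listed items hardly need a control group because they concern the interface or its delivery (intolerance from air leak, pressure sore or area, claustrophobia, oro-nasal dryness). Five others can be expected after open abdominal surgery whether or not CPAP is given: pain, vomiting, hypercapnia, haemodynamic instability and aspiration of gastric contents. That expectation is clinical judgement, as the SAP gives no background rates. If it is right, a CPAP-arm count of these items mixes background events with any effect of CPAP.

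Two mistakes become possible. A high count could be blamed on CPAP when it is mostly background, or a real excess could be dismissed as background. The data best placed to guard against both, the complications collected in both arms, would be reported without a between-arm estimate.

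**Working it through.** **1. Arm size, from the plan's own figures (section 4.3).** Inputs: 11.7% versus 8.8%, 90% power, two-sided 5%, 4% loss.

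n per arm = [1.960 × √(2 × 0.1025 × 0.8975) + 1.282 × √(0.117 × 0.883 + 0.088 × 0.912)]² / (0.117 − 0.088)² = 2297.

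Total 2 × 2297 = 4594, and 4594 / 0.96 = 4786. The plan's 4800 (2400 per group) reproduces, so 2400 per arm is used below.

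**2. What the one-arm data can say.** Take an illustrative rate of 10% in the CPAP arm. Its 95% half-width is 1.96 × √(0.10 × 0.90 / 2400) = 0.012, or 1.2 points. The rate itself is precise. The excess is the CPAP rate minus the background rate, and the background rate is not collected:

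| Assumed background | Excess at a 10% CPAP-arm rate |
|---|---|
| 0% | 10 points |
| 2% | 8 points |
| 5% | 5 points |
| 8% | 2 points |
| 10% | 0 points |

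A background above 10% would mean fewer events under CPAP, so zero is not a lower bound. More patients would narrow the 1.2 points but would not tell these rows apart.

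**3. Who and what the one-arm count covers.** The window runs for 24 hours from the end of surgery. Randomisation may take place up to four hours after surgery (section 4.2), so an event before allocation could be counted. Section 5.6 includes every CPAP-group patient with a recorded outcome, while sections 5.2.5 and 5.11 allow for patients in that group who receive no CPAP. The count is therefore of events after surgery in the allocated group, not strictly of events during CPAP.

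**4. What the two-arm complications could say.** Half-width of the 95% CI for a risk difference, with a common rate p in both arms: 1.96 × √(2p(1 − p) / 2400).

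| Assumed p | Half-width |
|---|---|
| 1% | 0.6 points |
| 2% | 0.8 points |
| 5% | 1.2 points |
| 10% | 1.7 points |

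With the planned 4% loss (2400 × 0.96 = 2304 per arm) these widen by a factor of √(2400 / 2304) = 1.02. The event rates are assumptions.

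**The case against.** The strongest reply is that harm is already compared between arms. Death, re-intubation, pneumonia, postoperative infection and mechanical ventilation are analysed as adjusted odds ratios with 95% CIs (sections 5.3 and 5.4, Table 5), and all p-values are two-sided. Aspiration that led to pneumonia, re-intubation or death would enter these analyses. Tables 6 and 8 also show aspiration pneumonitis, pneumothorax, arrhythmia and other complications by arm, so a reader can compute a crude difference from the counts. All of this stands. A reader might infer that the harm objective cannot be met, or that benefit is estimated and harm is not; the documents support neither. Aspiration pneumonitis is, however, only a partial counterpart to aspiration of gastric contents, because the event and the window (30 days against 24 hours) differ.

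Second, the appendix cited in section 3.4 may define the items narrowly or require attribution. Pain, for example, could mean pain from the interface. This cannot be checked from the SAP, and it limits the point.

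Third, declining to test is reasonable with 26 complication categories. That stands too, but an interval for a few pre-named items is not a test.

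Fourth, a reader might conclude that the five items should be recorded in usual care as well. That changes data collection and not the analysis, the SAP does not show that patients remain to be recruited, and under open allocation the recording could differ between arms. It is not recommended here.

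**Conclusion.** The point holds for five of the ten safety items. For pain, vomiting, hypercapnia, haemodynamic instability and aspiration of gastric contents, the plan yields incidence in the CPAP group within 24 hours of surgery and cannot yield an excess risk at any sample size. The four interface items and the related other harm are not affected.

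Two assumptions carry this: that these five events also occur after such surgery without CPAP, and that the appendix not shown imposes no attribution rule. If it does, the point weakens to one of labelling.

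No stated figure is wrong and the primary analysis is untouched. What is missing is a between-arm estimate for the complications closest to CPAP harm. The planned sample could give one to within about 0.8 to 1.7 points at event rates of 2% to 10%.

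**What to change.** 1. In section 5.7 and Table 6, pre-name a short list of plausible CPAP-related complications already collected in both arms, for example aspiration pneumonitis, pneumothorax, arrhythmia, anastomotic leak and perforation of viscus. Report each as a risk difference with 95% CI by allocated arm, labelled descriptive, with no hypothesis test. Fix the list before outcome data are inspected.
2. In section 3.4 and Tables 12 to 14, describe the one-arm results as *adverse events within 24 hours of surgery in the CPAP group*, and state that they do not estimate excess risk. If the appendix contains an attribution rule, state it there.

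The cost is SAP wording and one added column in Table 6, with no new data. The downside is a few intervals uncorrected for multiplicity. With five of them, and no true effect on any, the chance that at least one excludes zero is about 1 − 0.95⁵ = 23% if they are independent, which is why the descriptive label matters.

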4.1 Trial design

PRISM is an international, multi-centre, parallel group, randomised controlled trial with open study group allocation.

4.2 Randomisation

Randomisation will occur after the participant has provided informed consent and up to four hours after the end of surgery. Participants will be centrally allocated to treatment groups (1:1) by a computer-generated dynamic procedure (minimisation) with a random component. Minimisation variables will be country, surgical procedure category and planned use of epidural anaesthesia. The surgical procedure categories are as follows: (a) resection of colon, rectum or small bowel; (b) resection of liver, pancreas or gall bladder; (c) resection of stomach (non-obesity surgery); (d) resection of oesophagus (non-obesity surgery); (e) obesity surgery; (f) vascular procedure; or (g) other intra-peritoneal surgery. Each participant will be allocated with 80% probability to the group that minimises between group differences in these factors among all participants recruited to the trial to date, and to the alternative group with 20% probability. To enter a patient into the PRISM trial, research staff at the site will log on to a secure web-based randomisation and data entry platform and complete the patient's details to obtain a unique patient identification number and allocation to a treatment group.

4.3 Sample size

The primary outcome is a composite endpoint of pneumonia, re-intubation, or death within 30 days of randomisation. The incidence of postoperative pneumonia in previous trials was 8.0% in the usual care group and 4.3% (relative risk reduction of 46%) in the treatment arm. However, the total number of patients included in these five trials was less than 600 patients. The incidence of postoperative pneumonia, admission to intensive care (a surrogate marker of re-intubation) and death in a large international cohort (n ~9000) was 11.7% for patients aged over 45 years [1]. In order to detect a reduction from 11.7% to 8.8% in the primary outcome measure (relative risk reduction of 25%), with 90% power, a type I error rate of 5%, and a loss to follow up rate of 4%, we would require a total sample size of 4800 patients (2400 per group). This sample size will allow us to detect a 26% relative risk reduction (7.7% vs. 5.7%) in the secondary outcome measure of mortality at one year after randomisation, with 80% power and a type I error rate of 5%. The sample size was calculated, using the *'power two proportions'* function in STATA 14.0 (StataCorp, College Station, USA).

5. Analysis Principles

5.1 General analysis principles

Analyses will follow the intention-to-treat principle: all randomised patients with a recorded outcome will be included in the analysis, and analysed to the treatment to which they were randomised [2, 3]. Patients will be included in the analysis, regardless of whether the treatment they received was compliant with the protocol. Patients with missing outcome data will be excluded from the analysis. Definitions of what constitutes a recorded outcome for each outcome can be found In Appendix 1. Patients who are re-randomised (i.e. enrolled in PRISM for a repeat surgery despite previous enrolment in PRISM) will be included in the analysis for both randomisations, and treated as independent observations [4, 5].

The magnitude of treatment effect estimate will be reported with 95% confidence interval for primary and secondary outcomes. All p-values will be two-sided, and a significance level of 5% will be used. For each outcome, summary statistics (e.g. mean (SD), number (%)) will be presented separately for each treatment arm.

5.2 Initial descriptive analysis

5.2.1 Representativeness of patients

All participating sites have been asked to keep a log of eligible patients not recruited to the trial. Reasons for non-participation will be categorised and summarised. Participation in the trial, treatment allocation and completeness of follow-up will be illustrated by a CONSORT flow diagram.[6]

5.2.2 Comparability of groups

Baseline demographic and clinical data for patients randomised to CPAP (treatment group) and usual care (usual care group) will be summarised but not subjected to statistical testing. Numbers (%) and means (SD) or medians (IQR) will be provided separately for each group. The treatment and usual care groups will be compared at entry for the following baseline characteristics:

- Demographic: age (years), gender (male/female)
- Co-morbid disease: (a) COPD; (b) asthma; (c) interstitial lung disease or pulmonary fibrosis; (d) bronchiectasis; (e) ischaemic heart disease; (f) diabetes mellitus; (g) heart failure; (h) liver cirrhosis; (i) active cancer; (j) previous stoke or TIA; (k) respiratory infections within the previous month; (I) HIV
- Current smoker
- ASA grade: I; II; III; IV

- Body mass index (kg/m^2)
- Minimisation criteria:
 - Planned surgical procedure: (a) resection of colon, rectum or small bowel; (b) resection of liver, pancreas or gall bladder; (c) resection of stomach (non-obesity surgery); (d) resection of oesophagus (non-obesity surgery); (e) obesity surgery; (f) vascular surgery; (g) other intra-peritoneal surgery
 - Country: (a) Italy; (b) Spain; (c) Sweden; (d) United Kingdom; (e) South Africa; (f) Norway
 - Planned use of epidural
- Surgical procedure performed: (a) Resection of colon, rectum or small bowel; (b) resection of liver, pancreas or gall bladder; (c) resection of stomach (non-obesity surgery); (d) resection of oesophagus (non-obesity surgery); (e) obesity surgery; (f) vascular procedure; (g) other intraperitoneal surgery
- Pre-operative blood tests results: (a) haemoglobin (g/dL); (b) creatinine (μmol/L)
- ARISCAT score: ARISCAT is a risk index based on seven patient factors that evaluates risk for postoperative pulmonary complications in a patient [7, 8]. The seven factors are used to calculate this score are: age, oxygen saturation measured by pulse oximetry (SpO₂, %), pre-operative haemoglobin concentration, respiratory infection in the last month (yes/no), surgical incision category (peripheral/abdominal/thoracic), duration of surgery (hours) and emergency procedure (yes/no). ARISCAT score will be calculated for both groups and presented in the baseline data table. The component variables will be tabulated separately for reference. The ARISCAT Score and its individual components will only be summarised for patients who have all components of the score complete.

5.2.3 Clinical management

Clinical management for the treatment group and usual care group will be summarised but not subjected to statistical testing. Numbers (%) and means (SD) or medians (IQR) will be provided separately for each group. The treatment and usual care groups will be compared for the following clinical management characteristics:

- Surgery: open surgical technique; anaesthetic technique; mechanical ventilation during surgery
- Intravenous fluids during surgery: total intravenous fluid administered excluding blood products; total volume of blood products administered
- Planned and actual level of care on the first night after surgery
- Respiratory support after surgery within four hours of the end of surgery

5.2.4 CPAP after surgery

CPAP information for the CPAP group will be summarised. For each, summary statistics (e.g. mean

(SD), median (IQR), number (%)) will be presented. The following CPAP characteristics will be reported:

- Duration of CPAP within 12 hours of the end of the surgery (minutes)
- Maximum airway pressure received within 12 hours after the end of surgery (cmH₂O)
- Primary method of CPAP delivery: face mask, helmet device, nasal mask

5.2.5 Protocol compliance

Numbers and percentages of protocol deviations will be reported. The following protocol deviations will be reported:

- Failure to administer CPAP to a patient in the treatment group
- Starting CPAP at a dose other than 5cmH₂O for a patient in the treatment group
- Administration of CPAP for less than 4 hours duration in the treatment group
- Administration of CPAP with significant interruption for a patient in the treatment group (continuous interruption of more than 15 minutes would usually be considered prolonged).
- Administration of CPAP to a patient in usual care group

We will report the number of patients in each treatment group with at least one of the above protocol deviations. In addition, a separate table as described above will be reported by the method which CPAP was delivered.

